## **8.5 Study size**

The sample size calculation is based on the primary objective to evaluate the safety and tolerability of Tresiba®. A sample size of 1000 patients, assuming 20% dropouts who have been exposed to insulin degludec during the treatment will provide a probability of 80% of detecting at least one event that occurs with an incidence of 2 in 1000 patients or approximately 6 events with an incidence of 1/100 patients.

For an unobserved event, with the above sample size the upper limit of the 95% CI of the rate would be 0.375 per year. In other words for an unobserved event, a rate of 0.375 per year or larger can be excluded with 95% probability.

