### **7.3 Endpoints**

Primary endpoint

- Incidence of AEs by preferred term during 1 year of treatment

Secondary safety endpoint

- Incidence of the following events during 1 year of treatment:
  - SAEs by preferred term
  - SADRs by preferred term
  - ADRs by preferred term
  - Severe hypoglycaemia

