### **8.2 Setting**

#### **8.2.1 Number of patients to be studied**

Planned number of patients to be included: 1000

Planned number of patients to complete the study: 800

Anticipated number of patients to be included in each country: India only-1000

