### **8.7 Data analysis**

No formal statistical testing will be done in this non-interventional trial.

All continuous and categorical endpoints will be analysed using descriptive statistics

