### **8.7.2 Statistical methods**

The primary endpoint will be summarized using descriptive statistics by SOC and preferred term showing number of subject with events, number of events, incidence rate and rate per 100 PYE. Exposure to be used in the calculation in rate should be defined as the timeframe from time of first Tresiba® dose to last contact in this PMS/PASS trial. All secondary endpoints related to AEs (ADR/SADR/SAEs) will be presented in a similar way.

These endpoints will also be presented by the severity grade.

Hypoglycaemic episodes will be summarised in a similar way presenting confirmed and severe episodes separately.

The continuous variables HbA1c and FPG, demographic data will be summarized with descriptive statistics (N, N miss (number of missing values), mean, standard deviation, and median). Baseline, end of trial values and change from baseline values will be presented. Missing values will be subject to last observation carried forward (LOCF)

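### Section 8.5 gives the upper 95% limit for an unobserved event as 0.375 per year; the protocol's own inputs give 0.375 per 100 patient-years, so the figure is 100 times too large as worded

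*Protocol*

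**What the plan says.** Section 8.5 starts from this basis: "A sample size of 1000 patients, assuming 20% dropouts who have been exposed to insulin degludec during the treatment". Section 8.2.1 gives the matching count: "Planned number of patients to complete the study: 800". The primary endpoint in section 7.3 fixes the period: "Incidence of AEs by preferred term during 1 year of treatment".

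Section 8.5 then makes two kinds of statement about what this size can show. The first concerns detection, including a "probability of 80% of detecting at least one event that occurs with an incidence of 2 in 1000 patients". The second concerns exclusion: "For an unobserved event, with the above sample size the upper limit of the 95% CI of the rate would be 0.375 per year". It is restated at once in other words: "a rate of 0.375 per year or larger can be excluded with 95% probability".

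In the analysis, section 8.7.2 summarises adverse events by "number of subject with events, number of events, incidence rate and rate per 100 PYE", so the rates in the report will be on a per-100 patient-year scale.

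**The concern.** A rate of 0.375 per year, read per patient, is more than one event for every three patients followed for a year. A safety study of 1000 patients would not be needed to rule that out. The figure also sits badly with the detection statement just before it, which credits the same study with a good chance of seeing an event that affects 2 patients in 1000.

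The study has no comparator and plans no formal testing. The detection and exclusion statements in section 8.5 are therefore its only quantitative account of what it can establish, and the exclusion bound is what gives meaning to an adverse event that is never seen. If the sentence is taken literally, an ethics committee or regulator is told that the study can exclude only very common events. If it is copied into the report, an unobserved event would be described with a bound that is too large by two orders of magnitude.

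**Working it through.** **Inputs.** 1000 patients and 20% dropout (section 8.5); 800 completers (section 8.2.1); one year of treatment (section 7.3); zero observed events and 95% confidence (section 8.5). Taking 800 patients for one year as 800 patient-years assumes that dropouts contribute nothing.

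**Step 1: confirm that section 8.5 works with 800.** The probability of at least one event at incidence 0.002 is 1 − 0.998^n.
- n = 800: 1 − 0.998^800 = 0.798, which matches the stated 80%.
- n = 1000: 1 − 0.998^1000 = 0.865, which does not.

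The companion figure of about 6 events at 1/100 also fits n = 800 if it is read as at least 6 events with the same probability: P(X ≥ 6) = 0.810 for a binomial with n = 800 and p = 0.01.

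**Step 2: reproduce the digits of the exclusion figure.** With zero events in T patient-years, the one-sided 95% upper bound is −ln(0.05)/T, or about 3/T (the rule of three).
- Rule of three: 3/800 = 0.00375 per patient-year = 0.375 per 100 patient-years.
- Exact Poisson: −ln(0.05)/800 = 0.003745.
- Exact binomial: 1 − 0.05^(1/800) = 0.003738.

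The digits 375 are those of 3/800. The stated value is 0.375/0.00375 = 100 times the result.

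**Step 3: look for a reading that gives 0.375 per year.** The two-sided 95% upper limit with zero events is −ln(0.025)/T, or about 3.69/T. In the table, 900 patient-years assumes that the 200 dropouts contribute half a year each on average (800 + 200 × 0.5), and 1000 ignores the stated dropout.

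| Patient-years | One-sided 95%, per 100 PY | Two-sided 95%, per 100 PY |
|---|---|---|
| 800 | 0.374 | 0.461 |
| 900 | 0.333 | 0.410 |
| 1000 | 0.300 | 0.369 |

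Divided by 100, every entry lies between 0.003 and 0.005 per patient-year. If the rate were meant as a total for the whole cohort over its one year, the bound would be about 3 events (one-sided) or 3.69 (two-sided), which again is not 0.375.

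**Step 4: what 0.375 per patient-year would mean.** At that rate, 800 patient-years would be expected to yield 0.375 × 800 = 300 events. Excluding it after zero events needs only 3/0.375 = 8 patient-years.

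**Step 5: compare with the detection statement.** With 800 patients, an event with a true incidence of 1/100 would go entirely unseen with probability 0.99^800, about 0.0003. The first paragraph of section 8.5 therefore implies that an unseen event at 1% is effectively excluded, whereas the second says that only rates of 37.5% per year or more are.

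**The case against.** The best defence is that this is a unit slip that misleads nobody. The digits are correct, section 8.7.2 already works per 100 patient-years, and the sentence before it in section 8.5 shows the intended order of magnitude. The rates in the report will be calculated from the data and not from this sentence. Much of that stands: nothing in the design depends on the figure. It does not make the text right, because the same number and unit appear in two consecutive sentences, and a reader who takes only the exclusion statement has no means of seeing that a scale factor is missing.

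Three stronger readings are tempting, and the protocol does not support them.

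- *The sample size is wrong.* It is not. The detection figures reproduce with 800 patients (Step 1), and the exclusion figure does so once its unit is restored.
- *Using a one-sided bound is an error.* The protocol does not state sidedness; it is inferred from the match to 3/800. With zero events the lower limit is 0, so a one-sided 95% bound is legitimate, and the wording "a rate of 0.375 per year or larger can be excluded with 95% probability" fits it. The only weakness is the unqualified CI label, which many readers will take as two-sided. Against the two-sided limit, the stated figure is about 81 times too large (0.375/0.00461); the factor of 100 refers to the one-sided bound.
- *The study will report no confidence intervals.* Section 8.7 says: "All continuous and categorical endpoints will be analysed using descriptive statistics". Section 8.7.2 names no interval, but neither section rules one out. Interval methods are commonly left to a SAP, which may exist but was not available here, so silence in the protocol is not a fault.

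**Conclusion.** The point holds as an arithmetic error in wording. Both exclusion sentences in section 8.5 overstate the bound by a factor of 100; the likely cause is a lost per-100-patient-years qualifier or a lost percent sign. With zero events in 800 patient-years, the one-sided 95% bound is 0.375 per 100 patient-years and the two-sided 95% upper limit is 0.46 per 100 patient-years.

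The exact values rest on the assumption that dropouts add no exposure. Section 8.7.2 counts exposure up to last contact, so the achieved bound may be somewhat lower, as the table shows. The choice of exposure does not alter the conclusion about scale. The consequence is confined to how the study's precision is described: enrolment, the completer target, the endpoints and the analyses are unchanged.

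**What to change.** In section 8.5, restate both sentences in the corrected unit, for example: for an event not observed in 800 patient-years, the one-sided 95% upper bound of the rate is 0.375 per 100 patient-years (the upper limit of a two-sided 95% CI would be 0.46 per 100 patient-years), so a rate of 0.375 per 100 patient-years or more can be excluded with one-sided 95% confidence. Add that 800 patient-years counts no exposure from dropouts, and that the bound in the report should be recalculated from the exposure actually accrued.

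Exact 95% confidence intervals in the safety tables would be a useful option, but they are not required by this point and may already be planned in the SAP.

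The cost is two reworded sentences and one added note. No extra patients, visits, tests or analyses are needed.

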## **8.6 Data management**

Data management is the responsibility of Novo Nordisk Headquarters

### **8.6.1 Data management**

Data management will be carried out by Novo Nordisk or delegated under an agreement of transfer of responsibilities to an external CRO. Data will be processed using an Oracle-based, validated data management system. The patients will be identified by patient number, site, and study identification number. Appropriate measures such as encryption or deletion will be enforced to protect the identity of human patients in all presentations and publications as required by local/regional/national requirements.

Electronic data transfer of any CRF or patient related data must be approved by the responsible Data Management Unit(s). In cases where data is transferred via non-secure electronic networks, data must follow applicable data protection regulations. Appropriate measures such as encryption or deletion must be enforced to protect the identity of patients in all presentations and publications as required by local/regional/national requirements.

### **8.6.2 Case report forms and rules for completing**

Print legibly using a ballpoint pen. Ensure that all questions are answered and that no empty data blocks exist. Ensure that no information is recorded outside the data blocks.

If a test/assessment has not been done and will not be available, indicate this by writing “ND” (not done) in the respective answer field in the CRF. If the question is irrelevant (eg is not applicable) indicate this by writing “NA” (not applicable) in the respective answer field. Further guidance can be obtained from the instruction in the CRF.

By signing the affirmation statement, the physician confirms that the information is complete and correct.

### **8.6.3 Corrections to CRFs**

Corrections to the data on the CRFs must only be made by drawing a straight line through the incorrect data and by writing the correct value next to data that has been crossed out. Each correction must contain initials, date and explanation (if necessary) by the physician or the physician’s authorised staff. If corrections are made by the physician’s authorised staff after the date of the physician’s signature on the affirmation statement, the statement must be signed and dated again by the physician. Corrections necessary after the CRFs have been removed from the physician’s site must be documented on a Data Clarification Form (DCF). Such corrections must be approved by the physician or her/his authorised staff.

### **8.6.4 CRF flow**

The sponsor will provide the investigator with CRF. The investigator is to provide patient data according to the sponsor’s instruction, in the designated data collection form, compliant with Good Clinical practice/ GPP.

Physicians (or appropriately trained designee) will complete paper CRFs at each patient visit. These CRFs will be collected by the Novo Nordisk India or the CRO acting as Novo Nordisk representative upon completion. The method by which the CRFs are transmitted is dependent on the location of the site. Possible methods include fax, courier or post. Once received at the CRO, the information on the CRFs will be entered into the database and processed according to the data management plan. Physicians (or appropriately trained designee) will be encouraged to complete and send all relevant CRFs pertaining to each patient’s visit promptly.

### **8.7 Data analysis**

No formal statistical testing will be done in this non-interventional trial.

All continuous and categorical endpoints will be analysed using descriptive statistics

### **8.7.1 Evaluability of patients for analysis**

The following analysis sets are defined.

Safety Analysis Set (SAS): will consist of all patients who have received at least one dose of Tresiba® during this PMS/PASS.

Efficacy Analysis Set (EAS): will consist of all patients in the SAS who have at least one post-baseline measurement concerning HbA1c, FPG or confirmed hypoglycaemic event(s).

The descriptive analyses of AEs will be based on the SAS. Also demographic data will be presented using SAS.

The summaries of HbA1c, FPG and confirmed hypoglycaemic events will be based on the EAS.

### **8.7.2 Statistical methods**

The primary endpoint will be summarized using descriptive statistics by SOC and preferred term showing number of subject with events, number of events, incidence rate and rate per 100 PYE. Exposure to be used in the calculation in rate should be defined as the timeframe from time of first Tresiba® dose to last contact in this PMS/PASS trial. All secondary endpoints related to AEs (ADR/SADR/SAEs) will be presented in a similar way.

These endpoints will also be presented by the severity grade.

Hypoglycaemic episodes will be summarised in a similar way presenting confirmed and severe episodes separately.

The continuous variables HbA1c and FPG, demographic data will be summarized with descriptive statistics (N, N miss (number of missing values), mean, standard deviation, and median). Baseline, end of trial values and change from baseline values will be presented. Missing values will be subject to last observation carried forward (LOCF)

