### **8.4.1 Visit procedures**

In agreement with its observational nature, there are no interventions in standard care for this study. Any procedure ordered by the physician during this study will be according to routine practice. The patient will not be called in for premature discontinuation or for a missed visit. The primary reason (adverse drug reaction or other) for discontinuation must be specified in the CRF. Patients will be instructed to maintain a diary to record AEs, hypoglycaemic episodes and concomitant medications, and these data will be entered into the paper CRF (If available). The patient must be asked about adverse events during each contact (visit or telephone) with the physician or study site staff. This may be done by posing a simple question such as “have you experienced any problems since the last contact?”

A patient who meets all inclusion criteria and none of exclusion criteria will be enrolled in the study and assigned a patient number. Patients enrolled in the study will be provided with contact address (es) and telephone number(s) of the physician and/or site staff.

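### With 20% expected to leave early, the crude share of dosed patients understates the 1-year adverse event risk by roughly 5–18%; Section 8.7.2 should label it and add a censored 1-year cumulative incidence

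*Protocol*

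**What the plan says.** Section 7.3 sets the primary endpoint as "Incidence of AEs by preferred term during 1 year of treatment". The secondary safety endpoints (serious events, adverse reactions, serious adverse reactions and severe hypoglycaemia) use the same 1-year window.

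Section 8.7.1 fixes the population: "The descriptive analyses of AEs will be based on the SAS", and that set "will consist of all patients who have received at least one dose of Tresiba".

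Section 8.7.2 fixes the summaries of the primary endpoint, by system organ class and preferred term, "showing number of subject with events, number of events, incidence rate and rate per 100 PYE". It then defines the exposure used in the rate as running from the first dose to the last contact. It gives no denominator for incidence rate and does not say which of the four measures answers the 1-year endpoint. The AE-based secondary endpoints are presented in a similar way.

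On follow-up, Section 8.2.1 has "Planned number of patients to be included: 1000" and "Planned number of patients to complete the study: 800". Section 8.5 repeats the loss: "A sample size of 1000 patients, assuming 20% dropouts who have been exposed to insulin degludec during the treatment". Section 8.4.1 adds: "The patient will not be called in for premature discontinuation or for a missed visit".

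**The concern.** The endpoint asks what proportion of patients have a given event within a year. None of the four listed measures estimates that proportion while allowing for incomplete follow-up. The nearest is the undefined incidence rate. It is listed separately from the patient-year rate, and Section 8.5 uses incidence per number of patients, so the natural reading is a crude share of the Safety Analysis Set.

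In a crude share, a patient who leaves after two months stays in the denominator as one whole patient, and any event in the other ten months is missed. If dropout is unrelated to events, the share can only fall as more patients leave. In a study whose primary objective is safety, heavier loss to follow-up would then make the reported percentages look more favourable, and nothing in Section 8.7.2 warns the reader.

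**Working it through.** **Inputs from the protocol.** Enrolled 1000 and completing 800 (Section 8.2.1), hence 20% dropout (also Section 8.5). Denominator: all patients with at least one dose (Section 8.7.1), taken here as all 1000. Exposure for the rate: first dose to last contact (Section 8.7.2).

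**Not in the protocol, so assumed and varied.** When patients leave, the true 1-year incidence, and how events spread over the year. Dropout is taken as unrelated to events, and patients as observed up to dropout.

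**The plan's own figure.** Section 8.5 states an 80% probability of seeing at least one event with an incidence of 2 in 1000.

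- With n = 800: 1 − 0.998^800 = 79.8%, which reproduces the stated figure.
- With n = 1000: 1 − 0.998^1000 = 86.5%, which does not.

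The sizing therefore gives dropouts no credit at all, whereas a crude share counts each of them as a full patient.

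**Bias of the crude share.** Let F(t) be the true cumulative incidence by time t in years, I = F(1), and T the dropout time.

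- Expected crude share = 0.8 × I + 0.2 × E[F(T)]
- Relative understatement = 0.2 × (1 − E[F(T)] / I)

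E[F(T)] lies between 0 and I, so the understatement lies between 0% and 20% whatever the timing.

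With a constant hazard, F(t) = 1 − (1 − I)^t. For I = 10% and dropout uniform over the year, E[F(T)] = 1 − 0.1/0.10536 = 0.0509, where 0.10536 = −ln(0.9). The share is 0.08 + 0.2 × 0.0509 = 9.02%, an understatement of 9.8%. Other timings, same I:

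| Dropout timing | Crude share (true 10%) | Relative understatement |
|---|---|---|
| All at month 9 | 9.52% | 4.8% |
| Uniform over months 6–12 | 9.52% | 4.8% |
| Uniform over the year | 9.02% | 9.8% |
| All at month 3 | 8.52% | 14.8% |
| Uniform over months 0–3 | 8.26% | 17.4% |
| All at month 1 | 8.17% | 18.3% |
| All at day 0 (limit) | 8.00% | 20.0% |

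Per 1000 dosed, 100 truly affected patients would show as about 95 with late dropout and about 83 with early dropout.

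**Sensitivity to event pattern and frequency.**

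- Half of the events in the first 3 months, the rest spread evenly, dropout uniform: E[F(T)]/I = 0.625, so 0.2 × 0.375 = 7.5%.
- Constant hazard, uniform dropout, I = 50%: 8.9%. With I = 80%: 7.4%.

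**The patient-year rate under the same assumptions.** Take a true rate of 10 per 100 patient-years.

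- Uniform dropout: 800 + 200 × 0.5 = 900 patient-years, 90 events, 10.0 per 100.
- Dropout uniform over months 0–3: 800 + 200 × 0.125 = 825 patient-years, 82.5 events, 10.0 per 100.

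With a constant rate and dropout unrelated to events, this measure is not understated.

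**The case against.** The strongest reply is that exposure adjustment is already in the plan. The sentence that lists the incidence rate also lists a rate per 100 patient-years, and the next one ends exposure at last contact. A reader might infer that the whole primary analysis counts unseen time as event-free. The document does not support that: an early leaver contributes to the rate only the time actually followed. What remains is that a rate over observed time is not the proportion of patients affected within a year. If its numerator includes repeat events, it cannot be converted into that proportion.

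Second, the crude-share reading is an inference. The term is undefined in the protocol, and an analysis plan not at hand may define it. This stands, and the point is therefore put as the most natural reading, not as a stated rule.

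Third, a reader might take 10–18% as the settled size of the bias. That range needs dropout that is uniform or early and a constant hazard; late dropout or front-loaded events give about 5–7.5%. A harsher calculation, in which patients are seen only up to their last attended visit, leaves uniform dropouts with 0.2 × (0.25 × 0 + 0.25 × 0.25 + 0.5 × 0.5) = 0.0625 year on top of 0.80, so 0.8625 year on average, and a true 10% reads 8.6%. The protocol does not support that as the base case. Sections 8.4.1 and 10.3 require patients to be asked about events at every contact, telephone included. Section 8.4.1 also provides for a patient diary, and Section 10.3 sets serious event reporting by the physician's knowledge, not by visits.

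Last, the study is descriptive, has no comparator and no formal testing, is sized to detect at least one event, and discloses incomplete data as a limitation in Section 8.9. No decision rule turns on a shift of this size. That limits the weight of the point but does not make the crude share a 1-year risk.

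**Conclusion.** The point holds as an improvement to the primary summary. If incidence rate means the crude share of the Safety Analysis Set, it understates the 1-year risk by a relative 5–18% under plausible dropout timings and event patterns at 20% dropout, with bounds of 0% and 20%. The range rests on assumed dropout timing and hazard shape, which the protocol does not give, and on dropout being unrelated to events. If patients leave because of events that are never recorded, the understatement is larger. If they leave after an event that was recorded, that event is not lost to the share.

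A reader might go further and call the primary analysis wrong. The documents do not support that. The patient-year rate is sound on its own terms, and the crude count is a legitimate description if labelled. What is missing from the listed measures is an estimate of the quantity that Section 7.3 names, and the data for it are already planned.

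**What to change.** In Section 8.7.2:

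- Define incidence rate as patients with the event divided by the Safety Analysis Set, and label it as not adjusted for incomplete follow-up.
- Keep the rate per 100 patient-years as it stands.
- Add the 1-year cumulative incidence of the first event, with time from first dose and censoring at last contact. Use the Aalen-Johansen estimator with death as a competing event, or Kaplan-Meier if there are no deaths. Do this at least for any adverse event, serious events, adverse reactions, serious adverse reactions, severe hypoglycaemia and the common preferred terms.
- Report how many patients in the Safety Analysis Set had no adverse event assessment after the first dose.

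The cost is one paragraph and a few tables. The treatment start date is collected at Visit 1, last contact is already needed for exposure, and event onset should come from the adverse event forms, which also cover severe hypoglycaemia. No visits or patients are added. The downsides are that the reported incidence becomes slightly less favourable, and that censoring still assumes dropout is unrelated to events, so this does not cure informative loss.
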